6.11.5. Vital Signs and Other Physical Findings	28
6.11.6. Electrocardiograms	29
6.12. Subgroup Analyses.....	29
6.13. Protocol Violations.....	29
6.14. Interim Analyses and Data Monitoring	30
6.14.1. Safety Interim Analyses	30
6.14.2. Efficacy Interim Analyses.....	30

6.14.3. Pharmacokinetic/Pharmacodynamic Interim Analyses..... 31

6.15. Analyses for the Japanese Regulatory Authority 31

6.16. Annual Report Analyses..... 31

6.17. Clinical Trial Registry Analyses..... 31

7. Unblinding Plan..... 31

8. Changes to Planned Analyses in Protocol..... 34

9. References 35

10. Appendices 37

Redacted Version

Table of Contents

Table	Page
Table JPBM.6.1. Rules for Determining Date of Progression or Censor for Progression-Free Survival	17
Table JPBM.6.2. Example Nominal Significance Levels	22

Redacted Version

Table of Contents

Figure	Page
Figure JPBM.5.1.Illustration of study design.	10
Figure JPBM.6.1.Initial graph.....	20

Redacted Version

Table of Contents

Appendix		Page
Appendix 1.	Abemaciclib Consolidated AE Terms	38

Redacted Version

3. Revision History

Statistical Analysis Plan (SAP) Version 1 was approved prior to the first internal blinded safety review and the first unblinded safety analysis by the Data Monitoring Committee (DMC).

Statistical Analysis Plan Version 2 was approved after the third unblinded safety analysis by the DMC, but prior to unblinding of the sponsor and prior to the first interim analysis for efficacy.

The overall changes and rationale for the changes incorporated in Version 2 are as follows:

- Updates to the interim analysis plan and the analysis of overall survival in Protocol Amendment (a).

Statistical Analysis Plan Version 3 was approved after unblinded safety analyses by the DMC but prior to unblinding of the sponsor and prior to the first interim analysis for efficacy. The overall changes and rationale for the changes incorporated in Version 3 are as follows:

- Timing of final PFS analysis changed to 240 events and second interim analysis which was added with protocol amendment (a) was removed per amendment (b). Alpha spend for the interim was changed from 0.0001 to 0.00025.
- Updates to the overall survival analysis plan. Specifically, the pooled (JPBL and JPBM) overall survival analysis was reclassified as an exploratory analysis.
- Modification to the definition for baseline value of an efficacy assessment to include an assessment prior to first dose if no assessment prior to the date of randomization is available.
- Clarification to the definition of a treatment emergent adverse event.
- Inclusion of list of consolidated MedDRA preferred terms used for adverse event reporting.

Statistical Analysis Plan Version 4 was approved after unblinded safety analyses by the DMC but prior to unblinding of the sponsor and prior to the first interim analysis for efficacy. The overall changes and rationale for the changes incorporated in Version 4 are as follows:

- The OS analysis after 236 OS events was replaced by analyses after 189 and 252 OS events.
- A statement was added to specify the key quality of life items and domains for comparative statistical analysis to meet registration requirements.
- The list of consolidated MedDRA preferred terms was updated in Appendix 1 following medical review of observed adverse events.

Statistical Analysis Plan Version 5 was approved after unblinded safety analyses by the DMC but prior to unblinding of the sponsor and prior to the first interim analysis for efficacy. Version 5 updates the gated analysis of OS to split alpha between the ITT population and the population of patients with visceral disease at baseline.

4. Study Objectives

4.1. Primary Objective

The primary objective of this study is to compare treatment with abemaciclib plus nonsteroidal aromatase inhibitor (NSAI) therapy versus placebo plus NSAI therapy with respect to progression-free survival (PFS) in postmenopausal women with hormone-receptor positive (HR+), human epidermal growth factor receptor 2-negative (HER2-) locoregionally recurrent or metastatic breast cancer who have not received prior systemic therapy in this disease setting.

4.2. Secondary Objectives

The secondary objectives of the study are to compare the combination treatment of abemaciclib and NSAI therapy versus placebo plus NSAI therapy with respect to the following:

- overall survival (OS)
- overall survival rate at 1, 2, and 3 years;
- objective response rate (clinical response + partial response [ORR = CR + PR]);
- duration of response (DoR) for CR + PR;
- disease control rate (DCR = CR + PR + stable disease [SD]);
- clinical benefit rate (CBR = CR + PR + SD \geq 6 months);
- the safety and tolerability;
- change in symptom burden from baseline using the European Organization for Research and Treatment of Cancer Quality of Life Questionnaire Core 30 (EORTC QLQ-C30), EORTC QLQ-BR23 (breast) questionnaire, and health status scores from the EuroQoL 5-Dimension 5 Level (EQ-5D 5L);
- the pharmacokinetics (PK) of abemaciclib, its metabolites, and NSAI therapy.

4.3. Exploratory Objectives

[figure not shown]
- To explore potential biomarkers related to the mechanism of action of abemaciclib, the cell cycle, and/or the pathogenesis of breast cancer.
- To explore change in tumor size.

5. Study Design

5.1. Summary of Study Design

Study I3Y-MC-JPBM (JPBM) is a multicenter, randomized, double-blind, placebo-controlled, Phase 3 study evaluating treatment of abemaciclib with NSAI or placebo with NSAI in postmenopausal women with hormone receptor-positive (HR+), HER2- locoregionally recurrent (not amenable to curative therapy) or metastatic breast cancer who have not received prior systemic therapy in this disease setting.

Figure JPBM.5.1 illustrates the study design.

Abbreviations: HER2- = human epidermal growth factor receptor 2-negative; HR+ = hormone receptor-positive; N = number; NSAI = nonsteroidal aromatase inhibitor; PD = progressive disease; R = randomized.

Figure JPBM.5.1. Illustration of study design.

Approximately 450 patients will be randomized 2:1 between the 2 arms:

- Experimental Arm A: abemaciclib 150 mg orally every 12 hours on Days 1 to 28 plus either anastrozole 1 mg or letrozole 2.5 mg once daily of a 28-day cycle
- Control (Placebo) Arm B: placebo orally every 12 hours on Days 1 to 28 plus either anastrozole 1 mg or letrozole 2.5 mg once daily of a 28-day cycle.

Patients will be randomized using the following stratification factors: nature of disease (visceral metastases versus bone-only metastases versus other) and prior (neo)adjuvant endocrine therapy (aromatase inhibitor therapy versus other versus no prior endocrine therapy). The presence of visceral metastases refers to lung, liver, pleural, peritoneal, or adrenal gland involvement at the time of randomization. Prior (neo)adjuvant endocrine therapy refers to aromatase inhibitor

therapy (e.g., anastrozole, exemestane and letrozole) versus other (e.g., tamoxifen and fulvestrant) versus no prior endocrine therapy.

5.2. Determination of Sample Size

The study will enroll approximately 450 patients in 2:1 randomization.

A 2-look group-sequential design of the primary endpoint of investigator-assessed PFS will be used to accommodate an event-driven plan for the interim and final PFS analyses (see Section 6.7.2 for details). There is 1 planned interim analysis and 1 final analysis for PFS in this study. The interim analysis is planned to take place after approximately 189 investigator-assessed PFS events have occurred. The primary PFS analysis will be performed after 240 PFS events have occurred. The cumulative 1-sided type I error rate of .025 will be maintained using the method described in Section 6.7.2.2. Assuming a hazard ratio (HR) of 0.67, this sample size yields more than 80% statistical power to detect superiority of the abemaciclib plus NSAI arm over the placebo plus NSAI arm with the use of a 1-sided log-rank test and a type I error of 0.025. If the true median PFS for the placebo plus NSAI arm is 10 months, then the HR of 0.67 amounts to an approximately 5-month (50%) improvement in median PFS for the abemaciclib plus NSAI arm under an additional assumption of exponential survival distribution.

6. A Priori Statistical Methods

6.1. General Considerations

6.1.1. Populations

The **entered** population includes all patients who sign the informed consent document.

The **enrolled** or **intent-to-treat (ITT)** population includes all randomized patients.

The **visceral disease (VIS)** population includes all randomized patients with visceral disease at baseline as per CRF.

The **randomized and treated (RT)** population includes all randomized patients who received at least one dose of abemaciclib, placebo, or NSAID.

Unless otherwise noted, all disposition analyses will be performed on the entered population, all patient characteristic and efficacy analyses will be performed on the ITT population, and all safety and exposure analyses will be performed on the RT population. An alpha controlled OS analysis will be performed on the VIS population.

All analyses will be performed by treatment arm. Unless otherwise noted, all analyses on the ITT population will be performed by assigned treatment arm and all analyses on the RT population will be performed by actual treatment received.

6.1.2. Definitions and Conventions

Study drug refers to abemaciclib or placebo.

Study treatment refers to abemaciclib + NSAID or placebo + NSAID.

The **date of randomization** is the date the patient was randomly assigned to abemaciclib + NSAID arm or placebo + NSAID arm using the interactive web response system (IWRS).

The **date of first dose** is the date of the first dose of study drug or NSAID.

The **baseline value of a safety assessment** is the last value observed prior to the first dose of study drug or NSAID.

The **baseline value of an efficacy assessment** is the last value observed prior to the date of randomization. If a patient's first assessment occurs after randomization but prior to the first dose, this assessment will be used as the baseline.

The **study day of a safety event or assessment** will be calculated as:

- the difference between the date of the event or assessment and the date of first dose plus 1 for all events or assessments occurring on or after the day of first dose. For example, if an event occurs on 08JUN2014 and the date of first dose was 06JUN2014, the study day of the event is 3.

- the difference between the date of the event or assessment and the date of first dose for all events or assessments occurring before the day of first dose. For example, if an event occurs on 05JUN2014 and the date of first dose was 06JUN2014, the study day of the event is -1.

The **study day of an efficacy event or assessment** will be calculated as:

- the difference between the date of the event or assessment and the date of randomization plus 1 for all events or assessments occurring on or after the date of randomization.
- the difference between the date of the event or assessment and the date of randomization for all events or assessments occurring before the date of randomization.

One **month** is defined as 365/12 days.

Unless otherwise noted, **summaries of continuous variables** will include a mean, median, standard deviation, minimum, and maximum.

Unless otherwise noted, **summaries of categorical variables** will include the frequency and percentage (relative to the population being analyzed) of each category.

6.2. Handling of Dropouts or Missing Data

With the exception of dates, missing data will not be imputed. The method of imputation for any dates that are imputed is described in the relevant section.

6.3. Patient Disposition

A detailed description of patient disposition will be provided. It will include a summary of the number and percentage of patients entered into the study, rescreened after screen failure, enrolled in the study, treated in the study, reasons for discontinuation from study treatment (RT population only), and reasons for discontinuation from study (ITT population only). Reason for discontinuation from both study treatment and the study will be summarized by pre-determined categories. If the reason for discontinuation is adverse event (AE), the associated AE term will be reported.

6.4. Patient Characteristics

6.4.1. Demographics and Performance Status

Patient demographics will be summarized. Patient demographics will include the following:

- race
- ethnicity
- age
- country

- height
- weight
- body mass index (BMI)
- baseline Eastern Cooperative Oncology Group (ECOG) performance status (PS).

6.4.2. Baseline Disease Characteristics

Disease characteristics will be summarized. Disease characteristics will include the following:

- study entry diagnosis
- disease extent at study entry (de novo metastatic disease vs metastatic recurrent disease vs locoregionally recurrent disease)
- prior (neo)adjuvant endocrine therapy (aromatase inhibitor vs other vs none)
- prior (neo)adjuvant chemotherapy (yes or no)
- Disease Free Interval (DFI)
- nature of disease (visceral metastases, bone only metastases, or other)
- measurable vs bone only non-measurable disease
- number of organs involved (1, 2, or 3+)
- metastatic site
- estrogen receptor status
- progesterone receptor status.

Prior (neo)adjuvant endocrine therapy will be reported directly from the 'Prior Neo(adjuvant) Endocrine Therapy' electronic case (clinical) report form (eCRF).

Prior (neo)adjuvant chemotherapy will be reported based on data reported on the 'Prior Systemic Therapy' eCRF. Chemotherapy includes both cytotoxic and targeted agents.

Disease free interval (DFI) is defined as the period of time between the completion of adjuvant endocrine therapy and disease recurrence for those patients who received adjuvant endocrine therapy. It will be calculated based on data reported on the 'Prior Systemic Therapy' eCRF. It will be calculated as the progressive disease date – end date of therapy + 1. If only the month and year of a treatment date or progression date is available, the day will be imputed to the 15th. The median and range will be reported.

Nature of disease will be reported directly from the 'Nature of Disease' eCRF. Disease measurability and number of organs involved will be derived from the 'Target Tumor Identification and Results' and 'Non-Target Tumor Identification and Results' eCRFs at baseline. All patients with at least one lesion on the target lesion form will be counted as having

measurable disease. The number of organs involved will be derived from the location codes of the target and non-target lesions.

6.4.3. Historical Illnesses

Historical illnesses are clinically relevant events in the past that ended before the screening visit. Historical illnesses (using Preferred Term(s) [PTs] from the most current version of the Medical Dictionary for Regulatory Activities [MedDRA]) will be summarized.

6.4.4. Prior Therapies

Prior radiotherapy, surgery, and systemic therapy will be summarized. Prior radiotherapy and surgery will be categorized by reason for regimen. Prior systemic therapies will be categorized by type of regimen (endocrine therapy vs chemotherapy) and specific therapy. Frequency of each specific therapy will be tabulated within each type of therapy.

6.4.5. Post Study Treatment Discontinuation Therapies

Therapies received following study treatment discontinuation will be summarized by arm. Therapies will be summarized overall and by category: endocrine therapy or targeted/chemotherapy.

6.5. Treatment Compliance

Treatment compliance of abemaciclib/placebo will be measured by pill counts and summarized by cycle. Within each cycle, compliance will be calculated as the ratio of total dose taken to the total assigned dose (minus any dose adjustments and doses omitted/withheld for medical or logistical reasons). The total assigned dose for a patient with no adjustments, omissions, or extensions for logistical reasons is $150 \text{ mg per dose} \times 2 \text{ doses per day} \times 28 \text{ days} = 8400 \text{ mg}$.

Treatment compliance of NSAID will be measured based on pill count data (for those sites using Lilly supplied NSAID) or data reported on 'Exposure Compliance: NSAID' form (for those sites using locally supplied NSAID), and will be summarized by cycle. Within each cycle, compliance will be calculated as the ratio of the number of doses taken to the total number of assigned doses (minus any dose adjustments and doses omitted/withheld for medical or logistical reasons). The total assigned dose for a patient with no adjustments, omissions, or extensions due to logistical reasons is $1 \text{ dose per day} \times 28 \text{ days} = 28 \text{ doses}$.

6.6. Concomitant Therapy

All medications will be coded to the generic preferred name according to the current World Health Organization (WHO) drug dictionary. All concomitant medications will be summarized for the ITT population using the preferred name.

6.7. Efficacy Analyses

6.7.1. General Considerations

6.7.1.1. Population

Unless otherwise noted, all efficacy analyses will be performed on the ITT population.

6.7.1.2. Stratification Factors

The stratification factors for the analysis of primary and secondary analyses are:

- nature of disease (visceral metastases vs bone only metastases vs other)
- prior (neo)adjuvant endocrine therapy (aromatase inhibitor vs other vs none).

The stratification factors are captured in the IWRS and on electronic clinical (case) report forms (eCRFs). Unless otherwise specified, all stratified analyses will be based on the stratification factors per IWRS. A cross tabulation of the frequency of each level of each stratification factor per IWRS and eCRF will be produced.

6.7.1.3. Hypothesis Tests and Confidence Intervals for Efficacy Data

Unless otherwise noted, all hypothesis tests will be performed at the one-sided .025 level and all confidence intervals (CIs) will utilize a 95% confidence level.

6.7.2. Primary Endpoint: Progression-Free Survival

6.7.2.1. Definition

The primary efficacy measure is progression-free survival as defined by RECIST Version 1.1 and determined by the investigator. The PFS time is measured from the date of randomization to the date of objective progression or the date of death due to any cause, whichever is earlier.

If a patient is not known to have progressed or died at the time of analysis, PFS time will be censored at the last known progression-free assessment. The detailed censoring rules are described in the table below ([Table JPBM.6.1](#)).

Table JPBM.6.1. Rules for Determining Date of Progression or Censor for Progression-Free Survival

Rule	Situation	Date of Progression or Censor	Outcome
1	No baseline tumor assessments	Date of Randomization	Censored
2	No post baseline assessments and no death	Date of Randomization	Censored
3	No documented progression and no death (with a post-baseline tumor assessment)	Date of last adequate tumor assessment	Censored
4	Patient lost to follow-up (or withdrew consent from study participation) before documented progression or death	Date of last adequate tumor assessment	Censored
5	Documented progression	Date of documented progression. If a tumor assessment was done on multiple days, use the earliest date for that visit.	Progressed
6	Death without documented progression	Date of death	Progressed
7	Documented progression or death after missing ≥ 2 consecutive post-baseline tumor assessments	Date of last adequate tumor assessment before missed assessments or date of randomization, whichever is later	Censored

Note: Progression-free survival and associated outcome is determined by the earliest of the dates above, if more than 1 situation applies.

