12.2.6. Primary Outcome and Methodology

The primary endpoint of this study is PFS. PFS time is measured from randomization until the date of investigator-determined objective progression as defined by RECIST v1.1, or death from any cause. Patients who have neither progressed nor died will be censored at the day of their last radiographic tumor assessment, if available, or date of randomization if no post-initiation (that is, post-baseline) radiographic assessment is available. The detailed censoring rules are described in Table JPBM.12.1.

Table JPBM.12.1. Rules for Determining Date of Progression or Censor for Progression-Free Survival

Rule	Situation	Date of Progression or Censor	Outcome
1	No baseline tumor assessments	Date of Randomization	Censored
2	No post-baseline assessments and no death	Date of Randomization	Censored
3	No documented progression and no death (with a post-baseline tumor assessment)	Date of last adequate tumor assessment	Censored
4	Patient lost to follow-up (or withdrew consent from study participation) before documented progression or death	Date of last adequate tumor assessment	Censored
5	Documented progression	Date of documented progression. If a tumor assessment was done on multiple days, use the earliest date for that visit.	Progressed
6	Death without documented progression	Date of death	Progressed
7	Documented progression or death after missing >2 consecutive post-baseline tumor assessments	Date of last adequate tumor assessment before missed assessments or date of randomization, whichever is later	Censored

Note: Progression-free survival and associated outcome is determined by the earliest of the dates above, if more than 1 situation applies.

The PFS analysis to test the superiority of LY2835219 to placebo in improving PFS time will use the log-rank test stratified by nature of disease (visceral metastases versus bone-only metastases versus other) and prior (neo)adjuvant endocrine therapy (aromatase inhibitor therapy versus other versus no prior endocrine therapy). The Kaplan-Meier method (Kaplan and Meier 1958) will be used to estimate the PFS curves as well as PFS rates at every 3 months for each treatment group. These rates will be compared based on a normal approximation for the difference between the rates.

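### PFS censoring Rule 1 has no condition on death, so a patient without a baseline tumor assessment who dies is censored at randomization, against the plan's own PFS definition

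*SAP*

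**What the plan says.** SAP 6.7.2.1 runs PFS from randomization to "the date of objective progression or the date of death due to any cause, whichever is earlier". The next sentence says who is censored: "If a patient is not known to have progressed or died at the time of analysis, PFS time will be censored". Protocol 12.2.6 agrees: "Patients who have neither progressed nor died will be censored at the day of their last radiographic tumor assessment".

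The rules that matter in Table JPBM.6.1 are:

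- **Rule 1**, "No baseline tumor assessments": censored at randomization. Death is not mentioned.
- **Rule 2**, "No post baseline assessments and no death": censored at randomization. Rule 3 carries the same restriction on death.
- **Rule 6**, "Death without documented progression": an event at the date of death.
- **Rule 7**: progression or death after two or more consecutive missed post-baseline assessments is censored at the last adequate assessment or at randomization, whichever is later. The protocol's Rule 7 requires more than two missed assessments.
- **Note**: "Progression-free survival and associated outcome is determined by the earliest of the dates above, if more than 1 situation applies".

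Rule 1 and the note read the same in Protocol Table JPBM.12.1.

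**The concern.** A baseline scan is needed to judge whether a tumor has grown or a lesion is new. It is not needed to observe a death. As written, the table removes a known death from the primary endpoint, and the patient leaves the risk set at day 0. She stays in the ITT population by name but adds nothing to the log-rank test.

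The primary endpoint therefore has two possible derivations. A programmer who follows the text above the table counts the death, and one who follows the table drops it. Which applies should not be settled after treatment codes are known.

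PFS sensitivity analyses 1 to 4 (SAP 6.7.5.1) do not restore these deaths. The central-review PFS analysis is specified in a separate SAP that is not available here.

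**Working it through.** **Step 1: the rules side by side.** Take a randomized patient with no baseline assessment who dies without documented progression.

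| Source | Date | Outcome |
|---|---|---|
| PFS definition | death | event |
| Sentence on who is censored | not applicable, she is known to have died | not censored |
| Rule 6 | death | event |
| Rule 1 | randomization | censored |
| Table note (earliest date) | randomization | censored |

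Randomization precedes death, so the note always selects Rule 1. The note closes off the charitable reading that Rule 6 takes over.

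**Step 2: the plan's own power figure.** Inputs from SAP 5.2 are 240 events, HR 0.67, 2:1 allocation and 1-sided alpha 0.025. With Schoenfeld's formula:

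power = Φ(√(D·p(1−p))·|ln HR| − z)

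√(240 × 2/3 × 1/3) = 7.303; |ln 0.67| = 0.4005; 7.303 × 0.4005 − 1.960 = 0.965; Φ(0.965) = 0.833. This agrees with the stated figure of more than 80%. The final boundary recomputed from the interim alpha of 0.00025 at 189 of 240 events is 0.0249993, equal to the SAP's value.

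**Step 3: deaths affected.** The SAP's example in 6.7.3.3 assumes 47 and 95 deaths at the interim and final PFS analyses, that is 47/450 = 10.4% and 95/450 = 21.1%. The number of patients without a baseline, k, is not in the documents. I assume 2 to 9 (0.4% to 2% of 450).

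| k | Deaths at interim (k × 47/450) | Deaths at final (k × 95/450) | Power at 240 minus those deaths |
|---|---|---|---|
| 2 | 0.2 | 0.4 | 0.832 |
| 5 | 0.5 | 1.1 | 0.831 |
| 9 | 0.9 | 1.9 | 0.830 |

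The largest change is 0.833 − 0.830 = 0.003. In the extreme case where all nine die and none is replaced, 231 events give 0.818. The final analysis is triggered by counted PFS events, so lost deaths mainly delay the cutoff and do not shrink the event count.

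**Step 4: Rule 7.** The counts in Step 3 are upper figures for the assumed k and death rate. Protocol 10.1.1 schedules imaging at the end of Cycles 2, 4 and 6, about weeks 8, 16 and 24. A patient who is never scanned has missed two assessments by about week 16. After that, the SAP's Rule 7 would censor her death at randomization whatever Rule 1 says. Under the protocol's Rule 7 the limit is three missed assessments, about week 24. For never-scanned patients, correcting Rule 1 therefore recovers only early deaths.

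**Step 5: possible shift in the hazard ratio.** As a crude bound, suppose two lost deaths all fell in one arm. With an assumed 140 abemaciclib-arm events, the HR moves by a factor of about 1 − 2/140 = 0.986. With an assumed 90 to 100 placebo-arm events, it moves by up to about 1/(1 − 2/90) = 1.023. On the log scale these are about 0.014 and 0.023, against a standard error of 1/7.303 = 0.137.

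**The case against.** The case for leaving the rule alone has four parts.

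- **The group should be nearly empty.** Baseline imaging is required for every patient (Protocol 10.1.1), eligibility needs measurable or bone-only disease by RECIST (Protocol 7.1, criterion 4), and enrollment waivers are not permitted (Protocol 7). This stands, and it is why the point is minor.
- **The correction conditions on outcome.** Rule 1 now depends only on a fact fixed by first dose. With a no-death condition, patients without a baseline who die stay at risk until death, while survivors leave at day 0. The observation is correct. It does not make the change a real trade-off, because Rule 2 already handles deaths this way and the stated endpoint requires it.
- **Rule 7 would censor many of these deaths anyway.** This stands (Step 4). A claim that every death in this group is lost because of Rule 1 would be too strong.
- **The deaths are not lost to the trial.** They still count for OS (SAP 6.7.3.2). This is true, but it does not make the PFS rule consistent with its definition.

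A reader might also infer that Rule 1 is informative censoring that favors one arm. The documents do not support that. The rule applies alike in both arms and to survivors and deaths, and it would be informative only if a missing baseline were related to prognosis, on which there is no evidence.

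Nor does SAP Version 3's change to the baseline definition show that missing baselines were expected. Accepting an assessment made after randomization but before first dose (SAP 6.1.2) shrinks the Rule 1 group.

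**Conclusion.** The inconsistency is real and can be shown from the text alone: Rule 1 with the earliest-date note turns a death that the PFS definition counts as an event into censoring at day 0. The likely effect on the result is small: at most about 0.4 to 1.9 of 240 events, fewer after Rule 7, and a power change of well under 1 point. Those figures rest on an assumed 2 to 9 patients without a baseline, on the SAP's illustrative death count, and on these patients dying at the average rate. The direction of any bias cannot be determined. This is a low-priority correction that makes the derivation of the primary endpoint unambiguous. It is not evidence that the primary test is compromised.

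**What to change.** In SAP Table JPBM.6.1 and Protocol Table JPBM.12.1, limit Rule 1 to patients with *no baseline tumor assessment and no death*, in line with Rule 2. A death in a patient without a baseline then becomes an event at the date of death under Rule 6, subject to Rule 7. Add one sentence saying that without a baseline only death, and not a progression call, counts as the PFS event.

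Make the change before the sponsor is unblinded. Protocol 12.2.1 allows minor clarifications of analysis methods to be described and justified in the SAP up to that point.

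The cost is a short edit in two documents, with no change to design, alpha or data collection. Survivors without a baseline remain censored at day 0, as now. Duration of response borrows the PFS censoring rules (SAP 6.7.4.2) but should not change, since response cannot be judged without a baseline.
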